9.3.2 Central Committee Review

In order to ensure consistent and accurate application of the EORTC/MSG guidelines across all study patients, a Central Review Committee including Pediatric Oncologists and Pediatric Infectious Disease Specialists will be assembled. Through consensus meetings, committee members will review all data pertinent to the EORTC/MSG guidelines and determine whether a patient sustained a possible, probable or proven IFI during the study period. The following data for each study patient will be collected and available at the time of the review: pathology reports, all CT scan and MRI reports, fungal Gram stain and microbiology culture results, non-culture mycology testing results (i.e., Histoplasma urine antigens, cryptococcal CSF and serum antigens), ophthalmology exams, bronchoscopy reports, and dosing and duration of steroid exposures.

All reviewers will be blinded to the patient's antifungal exposures in order to limit any bias in determining the primary and exploratory endpoints.

9.3.3 Sample size with power justification

IFI incidence

There has never been a randomized prospective trial of anti-fungal prophylaxis in this population of patients. Consequently, it is difficult to measure the expected rate of IFI in the control arm. Pediatric patients have represented less than 10% of the subject population in all but one prospective trial to date.^{3,14,19,20,29,54} And every prospective trial to date has had > 50% of their patients undergoing lower-risk forms of transplantation, including matched sibling donor HCTs, and even autologous HCTs in some cases. Given these limitations, the incidence of IFI on these trials has ranged dramatically, from as low as 2.4% at 70 days,¹⁴ to as high as 25% at 180 days post HCT.²⁰ A simple calculation achieved by combining the results of the 3 trials with 180 day endpoints demonstrates that, in patients receiving fluconazole prophylaxis, there is an approximately 14.5% incidence of IFI at 180 days, while in those receiving mold-active prophylaxis (itraconazole or voriconazole) there was an approximately 9.1% incidence of IFI at 180 days.^{3,19,20} If there was an even split between the number of patients receiving fluconazole vs. a mold-active azole, then a very rough estimate of the IFI incidence at 180 days would be 10.9%. Since the distribution of IFIs post-

transplant is bimodal, with one main peak being during the neutropenic period immediately post-HCT,^{25,30,53} we would expect roughly half of this, or ~6% to occur during the first 42 days.

Other reports support the hypothesis that roughly half of the “early” (< 180 days post-HCT) IFIs occur within the first 6 weeks. Figure 1A from Wingard *et al.* demonstrates a cumulative incidence curve of IFI; while only the number at 180 days is reported, it is clear that there is a sharp rise between Days 0 and 42, followed by a slower rise from Day 42 to Day 180, so that roughly half of the IFIs have occurred by Day 42.³ Three retrospective reports show similar conclusions. Hovi *et al.* reported that 5 of 11 (45%) IFI that were found in pediatric allogeneic HCT recipients during the first year post-HCT occurred during the first 6 weeks post-HCT.²⁷ Dvorak *et al.* reported that 10 of 12 (84%) cases of IFI occurred in the first month after pediatric allogeneic HCT.²⁶ Benjamin *et al.* reported that, in pediatric patients undergoing unrelated or haploidentical HCT (the population in question in this trial), the number of patients with Aspergillosis or Candidiasis (the 2 most common IFIs) was 22 from Days 0 to 30 post-HCT, 25 from Days 31-100, and only 5 from Days 101-365.⁵⁵ Thus, in Benjamin *et al.* 22 of 52 (42%) total IFIs occurring within the first year post-HCT happened within the first 30 days. Combining the small numbers from each of these retrospective studies would suggest that 39 of 77 (51%) of IFIs during the first year post-HCT actually occur within the first 4-6 weeks. Furthermore, a query of the International Pediatric Fungal Network database demonstrates that from July 2008 to December 2010, there were 14 pediatric patients who developed an IFI within 180 days from HCT. Eight of these (57%) occurred by Day 42, 2 between Days 43 and 100, and 4 from Days 101 to 180 ([name], personal communication). This data provides justification of the use of one-half of the reported Day 180 incidences from the published prospective trial of Wingard *et al.*

However, it should be strongly stressed that these numbers were generated from trials involving a lower-risk patient population in which < 50% of the patients underwent alternative donor HCT, which is the study population proposed for this trial. None of the prospective trials report whether alternative donors demonstrated a higher incidence of IFI than matched-siblings, but based on the largest available series of retrospective data the risk of IFI at 1 year in alternate donors is ~2% higher than seen in matched-siblings.⁵⁶ Benjamin *et al.* report a greater difference between matched sibling donor recipients and alternative donor recipients of 16% vs. 22% (at 100 days),⁵⁵ but we will use the more conservative 2% estimate. Once again, based on a bimodal distribution, we would expect approximately half of that increased IFI incidence to occur early post-transplant, thus increasing our overall estimate to ~7%.

Another source of data to inform this estimate is the various retrospective studies that have been performed, although these have inherent biases. There have been three pediatric-specific studies, which unfortunately have used different end-point times and methods.^{26,27,55} One study demonstrated an 8.7% incidence of IFI at 30 days in a mixed-risk patient population utilizing fluconazole prophylaxis.²⁶ Another demonstrated a 10.9% incidence of IFI at 30 days in our exact population of high-risk patients, but utilizing low-dose amphotericin B as prophylaxis.⁵⁵ Another informative study involved a very high number (> 2500) of primarily adult patients undergoing transplant from alternative donors and demonstrated an approximately 8% risk of IFI at 365 days post-HCT.⁵⁶ However, this population included ~30% non-myeloablative HCTs, which have a very different pattern of IFI than those undergoing myeloablative transplant⁵⁷ (the study population for this trial), making it difficult to fully utilize this data. Another group of patients who appear to be at high-risk for the development of IFI post-HCT are those undergoing HCT utilizing an umbilical cord blood (UCB), likely due to the extended period of neutropenia commonly seen in these patients. A report by Sadfar *et al.* demonstrated that 12.4% of their UCB HCT patients had developed an IFI by Day 30, and 22.6% by Day 100.⁵⁸ The prospective trials to date have included very few UCB recipients, including only 2 of 600 in the trial by Wingard *et al.*³ Finally, a report analyzed the infectious complications of high-risk (unrelated donor) HCTs done on the NHLBI-funded trial of *ex vivo* T-cell depletion vs. standard cyclosporine and methotrexate for GVHD prophylaxis.³⁰ The methodology of this study did not report an IFI incidence at 180 days, but at the time of data censoring, 31% of patients had ultimately gone on to

develop an IFI. This highlights the elevated risk of IFI in this population of patients, and underscores the danger of utilizing data generated from a lower-risk population to inform an IFI estimate for this trial.

We determined the magnitude of absolute IFI risk reduction by starting with the rate of 4% seen in the trial by Wingard *et al.*³ On that trial, in the early post-HCT period only 2 infections were due to organisms other than *Candida* and *Aspergillus*, (which would thus also not be covered by caspofungin). There are several theories why patients receiving a mold-active agent developed breakthrough *Aspergillus* or *Candida*. One possible reason is the inherent variability in voriconazole pharmacokinetics (as noted above), which may have led to inadequate serum levels in a significant number of patients.^{5,49} We would not expect a similar problem utilizing caspofungin, which has very predictable pharmacokinetics,⁵⁹ even in the setting of renal or hepatic insufficiency. Another possible reason is that 36% of the IFIs occurred after premature withdrawal of voriconazole.³ Since echinocandins are generally exceptionally well-tolerated, we expect a lower rate of premature stoppage of caspofungin when compared to the azole group, a finding also demonstrated in the trial by Van Burik *et al.*¹⁴ Given these inherent benefits of the echinocandin class, we therefore expect that caspofungin's magnitude of benefit will be slightly higher than seen in trials of other mold-active agents.

Therefore, we assume that the incidence of IFI during the period at risk for the primary objective (Day 0 to Day 42) is 7% in the control patients (with fluconazole or voriconazole) and that the incidence of IFI is 2% with caspofungin prophylaxis, which is a clinically important decrease in the risk of IFI.

Sample Size and Estimated Power

Assuming the incidence of IFI during the period at risk for the primary objective (Day 0 to Day 42) is 7% in the control patients (with fluconazole or voriconazole) and that the incidence of IFI is 2% with caspofungin prophylaxis, we will require 560 randomized patients (approximately 280 per arm) to achieve 80% power at 2-sided alpha level of 0.05. The power consideration is based on a 2-sample log rank test comparing the time to (first occurrence of proven/probable) IFI. Time to IFI is assumed to follow an exponential distribution. The observation period for the primary endpoint is from Day 0 till Day +42 following high-risk allogeneic HCT. Under an exponential time-to-IFI model with these parameters, the incidence of IFI is distributed almost evenly during the at-risk period; for each one-third of at-risk period (~14 days), the incidence of IFI is 2.3%-2.4% for patients on the azole arm and is 0.66%-0.67% for patients on the caspofungin arm. A 5% exponential loss-to-follow-up during the at-risk period is also included in the power consideration. Considering up to 5% of the enrolled patients might be deemed ineligible, the maximum enrollment number is adjusted to 590. The expected number of IFI among 280 eligible azole arm patients is 19.6.

9.3.4 Analysis Plans

Descriptive Analyses

Standard descriptive statistics will be used to describe subjects' baseline characteristics and study outcome measures overall and within each treatment group. Summary statistics such as means, standard deviations, medians, and ranges will be produced for all measured variables. The balance of baseline measures across the treatment groups will be examined using appropriate two-sample tests.

Analysis for Primary Objective

For the primary endpoint, the at-risk period for IFI is from Day 0 until Day +42. Events that will shorten the at-risk IFI observation period (including death, withdrawal consent for data submission, or patient loss to follow-up) prior to Day +42 are expected to be rare. Since death (a true competing risk event) prior to Day +42 is expected to be rare, in the primary analysis all these events will be treated as censoring events and standard survival data methods will be performed. The primary analysis will be based on the principle of intention to treat (i.e., by the treatment assignment of patients at randomization, regardless of subsequent

compliance with the assigned treatment). All eligible and randomized patients with available IFI data will be included in this analysis. A modified intention to treat analysis which only includes patients who complied with the randomized treatment will also be performed as an exploratory analysis to evaluate whether its result differs from that of the intention to treat analysis. Kaplan-Meier curves will be used to estimate the time to onset of proven/probable IFI for patients randomized to the 2 arms. Log rank test will be used to compare the incidence of IFI between the 2 randomized arms during the at-risk period up to Day +42. The primary analyses will be performed at overall 2-sided alpha level of 0.05, with two planned interim efficacy analyses (see Section 9.3.5). Cox proportional hazards models will also be used to explore the treatment difference between the 2 arms on time to IFI with adjustment for covariates such as stratification factors or other potential risk factors.

Exploratory Analyses on Clinical Endpoints

For exploratory objective 1, to examine the longer term treatment effect, a similar log rank test will be performed comparing the incidence of proven/probable IFI between the 2 randomization arms by extending the observation period up to Day +100. For exploratory objective 2 & 3, log rank test will be used to compare the incidence of proven/probable IFI of patients randomized to caspofungin within the particular randomization stratum defined by the comparator (fluconazole or voriconazole) to that of patients randomized to the comparator within the same stratum. For exploratory objective 4 on fungal-free-survival, failures for this endpoint will include death or proven/probable invasive fungal infection. Log rank test will be used to explore any treatment differences between the 2 arms on fungal-free-survival. For exploratory objectives 1-4, Cox proportional hazards models will also be used to examine the treatment difference between the 2 arms on time to IFI or fungal-free-survival with adjustment for other risk factors. For exploratory objective 5, the binary incidence of acute GVHD and the percentage distribution of acute GVHD by stage and by overall clinical grade will be estimated for each arm and compared between the 2 arms by Chi-square test. Logistic regression models (for the binary GVHD incidence data) or proportional odds models (for the ordinal GVHD data by stage or overall clinical grade) will also be used to explore the treatment difference between the 2 arms with adjustment for other risk factors such as donor HLA match score.

Based on the survey we performed, we expect about half of the enrolled patients will use fluconazole as the comparator and the other half will use voriconazole as the comparator. For the exploratory objective on comparing the incidence of IFI during the first 42 days between caspofungin and fluconazole or between caspofungin and voriconazole, with 140 patients per arm, the power to detect a difference in IFI incidence of 7% (comparator) vs. 2% (caspofungin) will be only about 51%. The power for a difference in IFI incidence of 7% (comparator) vs. 1% (caspofungin), 8% (comparator) vs. 2% (caspofungin), and 9% (comparator) vs. 2% (caspofungin) are 71%, 62%, and 71% respectively. These power considerations follow the same assumptions as those for the primary objective. For the exploratory objective on comparing the incidence of IFI during the first 100 days following high risk allogeneic HCT using the entire study population, assuming IFI incidence of 12% (with fluconazole or voriconazole) vs. 5% (caspofungin), the power to detect the difference is 81%. The incidence of IFI during this longer at-risk-period might be bimodal with the main peak during neutropenic period immediately after HCT; however due to lack of good estimate for such bimodal distribution, this power consideration is still based on exponential models and the incidence is distributed roughly evenly under these incidence assumptions. The power consideration for IFI up to Day 100 also includes a 15% exponential loss-to-follow-up. When only comparing patients randomized between caspofungin and one comparator (fluconazole or voriconazole), again with about half of the sample size (about 140 per arm), the power to detect IFI incidence during the first 100 days of 12% (comparator) vs. 5% (caspofungin) is only 52%. The power will be about 78% if the IFI incidence during the first 100 days is 14% (comparator) vs. 3% (caspofungin).

Analysis of beta-D Glucan Assay

Sensitivity, specificity, positive predictive value, and negative predictive value of the beta-D glucan assay will be determined using standard formulas and EORTC/MSG criteria as the gold standard. Please see Section 13.9 for additional statistical considerations for this aim.

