9.3 Statistical Analysis Methods

9.3.1 Study Endpoints

Primary endpoint

The primary endpoint is the development of proven or probable IFI defined according to criteria developed by the European Organization for Research and Treatment of Cancer/Mycoses Study Group (EORTC/MSG) (from which time to IFI will be computed).³¹ These definitions have been used in major trials of antifungal drug efficacy, in strategy trials, for formulating clinical practice guidelines, for validating diagnostic tests, as well as for undertaking epidemiologic studies. A Data Review Committee, blinded to study drug assignment, will review all clinical documentation used to determine the presence of an IFI and classify it based on the EORTC criteria. The period at risk for primary IFI endpoint will begin at Day 0 and extend until 42 days following stem cell infusion. Some patients at high-risk for IFI may have prolonged inpatient stays, but in order to obtain a relatively homogenous duration of study drug administration, Day +42 was chosen as the maximal period of administration, as was done in the micafungin trial. Based on intent-to-treat principle, the at-risk period will be the same for patients who terminated protocol prophylaxis prior to Day +42 (due to withdrawal or discharge) as long as data regarding IFI are available. For the primary endpoint, deaths that occur in the absence of proven/probable IFI will be counted as censoring events; as a comparison, for the exploratory endpoint of fungal-free-survival (see below), deaths without proven/probable IFI will be counted as events.

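### Deaths without IFI are censored and the primary endpoint is estimated by Kaplan-Meier, which overstates absolute IFI incidence; the plan is silent on the Day 100 estimator and on how deaths are handled there

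*Combined protocol and SAP*

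**What the plan says.** The primary objective (Section 1.1.1) and the first exploratory objective (Section 1.2.1) ask whether caspofungin lowers the incidence of proven or probable IFI by Day 42 and Day 100.

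**Day 42.** Section 9.3.1 states that "deaths that occur in the absence of proven/probable IFI will be counted as censoring events". Section 9.3.4 gives the reason: "Since death (a true competing risk event) prior to Day +42 is expected to be rare", so "in the primary analysis all these events will be treated as censoring events and standard survival data methods will be performed". On estimation, "Kaplan-Meier curves will be used to estimate the time to onset of proven/probable IFI for patients randomized to the 2 arms". On testing, "Log rank test will be used to compare the incidence of IFI between the 2 randomized arms during the at-risk period up to Day +42".

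**Day 100.** Section 9.3.4 (exploratory analyses) says that "a similar log rank test will be performed comparing the incidence of proven/probable IFI between the 2 randomization arms by extending the observation period" to Day +100, and adds Cox models. It does not name an estimator of incidence, restate what happens to deaths, or argue that deaths are rare over the longer window.

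**Elsewhere.** Fungal-free survival, with death as an event, is an exploratory endpoint at both times. Section 9.3.5 refers the study to the DSMC for possible closure if a one-sided 95% confidence interval for the comparator arm's Day 42 incidence excludes 7%, and notes that the exact rule depends on the amount of censoring. No cumulative incidence function appears anywhere in the plan, and no expected death rate is given.

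**The concern.** A patient who dies without IFI can no longer develop one. Censoring that death treats the patient as if still at the same risk as the survivors, and Kaplan-Meier passes the missing follow-up on to them. The resulting curve answers a hypothetical question, whereas the objectives concern the proportion of transplanted children who actually get an IFI.

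What is at stake is the absolute incidence in each arm, the risk difference built from it, and the comparator-arm check in Section 9.3.5. The excess grows with the number of deaths. Its effect on the arm difference depends on how deaths without IFI split between the arms. The rarity argument is the only protection offered, and it is written for Day 42 alone.

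**Working it through.** **1. The plan's own power figures.** Set the window length to 1 and take λ = −ln(1 − IFI risk) and η = −ln(1 − loss). The chance of an observed event is p(λ) = λ/(λ+η) × [1 − exp(−(λ+η))]. The Lachin-Foulkes form is

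power = Φ{ [λ₁ − λ₂ − 1.96·√(2λ̄²/(n·p(λ̄)))] / √[(λ₁²/p(λ₁) + λ₂²/p(λ₂))/n] }.

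Inputs from Section 9.3.3: 7% vs 2%, 5% loss, n = 280 per arm.

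- λ₁ = 0.0726, λ₂ = 0.0202, η = 0.0513
- p(λ₁) = 0.0683, p(λ₂) = 0.0195
- λ̄ = 0.0464, p(λ̄) = 0.0442
- (0.0524 − 1.96 × 0.01865)/0.01872 = 0.845, so power is 80.1%, against 80% stated

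The Day 100 inputs in Section 9.3.4 (12% vs 5%, 15% loss) give 81.1%, against 81% stated. Both figures reproduce.

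**2. What Kaplan-Meier reads for a given true incidence.** Let F₁ be the true proportion with IFI and F₂ the proportion dying first without IFI, with constant hazards. Then

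- total hazard H = −ln(1 − F₁ − F₂)
- IFI hazard = H × F₁/(F₁ + F₂)
- 1−KM = 1 − exp(−IFI hazard)

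F₁ is the plan's design rate. F₂ is an assumption, the same in both arms and shown as a range, because the plan gives no death rate.

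| Window | True F₁ | Deaths F₂ | H | IFI hazard | 1−KM |
|---|---|---|---|---|---|
| Day 42 | 7% | 5% | 0.1278 | 0.0746 | 7.2% |
| Day 42 | 7% | 10% | 0.1863 | 0.0767 | 7.4% |
| Day 100 | 12% | 10% | 0.2485 | 0.1355 | 12.7% |
| Day 100 | 5% | 10% | 0.1625 | 0.0542 | 5.3% |
| Day 100 | 12% | 20% | 0.3857 | 0.1446 | 13.5% |
| Day 100 | 5% | 20% | 0.2877 | 0.0575 | 5.6% |

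The Day 100 rows apply only if Kaplan-Meier is used there. In that case a true difference of 7.0 points reads as 12.7 − 5.3 = 7.4 with 10% deaths and 13.5 − 5.6 = 7.9 with 20%.

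**3. The reverse direction, with unequal deaths.** Suppose 1−KM reads 12% and 5% at Day 100. With λ = −ln(1 − p) and μ = −ln(1 − d), where d is the death risk in the absence of IFI, cumulative incidence is λ/(λ+μ) × [1 − exp(−(λ+μ))].

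- Azole (λ = 0.1278): 11.40% if d = 10%, 10.78% if d = 20%
- Caspofungin (λ = 0.0513): 4.75% if d = 10%, 4.49% if d = 20%

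A 7.0-point Kaplan-Meier difference is then 10.78 − 4.75 = 6.0 points if deaths are 20% azole and 10% caspofungin, and 11.40 − 4.49 = 6.9 points if reversed.

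**4. Early infections, late deaths.** Apply the step 3 formula in two stretches (Days 0–42 and 42–100), with azole Kaplan-Meier risk 7% then 12% and deaths 3% then 20%. Cumulative incidence is 11.31%, an excess of 0.7 points, against 12 − 10.78 = 1.2 points under constant hazards.

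**5. Power on the two scales.** With 5% deaths added to 5% loss at Day 42, power is 79.1% whether computed on cause-specific hazards or on cumulative incidence. With 15% deaths added to 15% loss at Day 100 it is 78.1% and 77.8%.

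**The case against.** The case on the other side is substantial, and most of it stands.

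- **The primary inference is comparative.** It rests on a log-rank test. With deaths censored, the log-rank and Cox analyses validly compare cause-specific hazards. A reader might infer that the primary test is invalid or the trial underpowered; steps 1 and 5 do not support that.
- **The plan is open about the issue.** It names death as a competing risk, gives its reason for censoring, and sets fungal-free survival beside the primary endpoint. That endpoint would show an excess of deaths in one arm, but it is a composite and does not estimate IFI incidence.
- **The Day 42 bias is small.** It is at most about 0.4 points on azole with up to 10% deaths. The standard error of a 7% rate in 280 patients is √(0.07 × 0.93/280), about 1.5 points.
- **Kaplan-Meier at Day 100 is not stated.** A reader might infer it from the word similar, but Section 9.3.4 names Kaplan-Meier only under the primary objective. The documents show a gap at Day 100, not a stated choice of estimator. The Day 100 endpoint is also exploratory.
- **The loss allowance is not evidence of mortality.** It rises from 5% at Day 42 to 15% at Day 100 ("The power consideration for IFI up to Day 100 also includes a 15% exponential loss-to-follow-up"), and a reader might take that as a sign of deaths. The plan does not say that deaths are included. A constant rate losing 5% in 42 days already loses 1 − 0.95^(100/42) = 11.5% in 100 days.
- **The arm difference is not always stretched appreciably.** With more deaths on caspofungin, step 3 gives 6.9 points against 7.0.

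What remains is that, where the plan names an estimator, it is one that overstates incidence, and that its rarity argument does not reach Day 100. The only mortality figure near that time is in Section 2.3.1: 20% of fluconazole recipients dead by Day 110 in an older trial of autologous and allogeneic patients over 12 years. At a constant rate this is 1 − 0.8^(100/110), about 18% by Day 100. The population differs and the figure covers all deaths, so it only helps to set the range.

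**Conclusion.** The point holds for absolute incidence. At Day 42 the plan censors a competing event and uses an estimator that overstates IFI incidence, by 0.2 points on azole with 5% deaths and 0.4 with 10%. At Day 100 neither the estimator nor the handling of deaths is specified. If Kaplan-Meier were used, the excess would be 0.7 points on azole and 0.3 on caspofungin with 10% deaths, and 1.5 and 0.6 with 20%; it would be smaller if infections come early and deaths late. These sizes rest on assumed death rates, constant hazards and, in the main table, equal deaths in the two arms. The size and importance of any distortion in the arm difference depend on deaths by arm, which the plan does not project.

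The log-rank test, the Cox models, the stated power and the sample size are not in question. This is a cheap improvement to estimation and reporting, not a flaw in the trial's primary test.

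**What to change.** In Section 9.3.4:

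- Estimate IFI incidence in each arm, and the arm difference with its confidence interval, at Day 42 and Day 100 by the Aalen-Johansen cumulative incidence function. Treat death without IFI as a competing event, and censor only loss to follow-up and withdrawal of consent.
- State the rule for deaths at Day 100 explicitly.
- Keep the log-rank test as the primary test, labelled as a comparison of cause-specific hazards. Gray's test may be reported beside it but is optional.
- State whether the 5% and 15% loss allowances include deaths.

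In Section 9.3.5, use the same estimator for the comparator-arm incidence check. With no loss to follow-up it reduces to the simple proportion, which is how the plan already words its approximate limits (2 of 93 and 7 of 187).

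The cost is a few sentences in the plan and a few lines of code. No new data are needed, because fungal-free survival already requires time to death.

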3.2 Patient Eligibility Criteria

Important note: The eligibility criteria listed below are interpreted literally and cannot be waived (per COG policy posted 5/11/01). All clinical and laboratory data required for determining eligibility of a patient enrolled on this trial must be available in the patient's medical/research record which will serve as the source document for verification at the time of audit.

All clinical and laboratory studies to determine eligibility must be performed within 7 days prior to enrollment unless otherwise indicated. Laboratory values used to assess eligibility must be no older than seven (7) days at the start of therapy. Laboratory tests need not be repeated if therapy starts within seven (7) days of obtaining labs to assess eligibility. If a post-enrollment lab value is outside the limits of eligibility, or laboratory values are > 7 days old, then the following laboratory evaluations must be re-checked within 48 hours prior to initiating therapy: bilirubin, ALT (SGPT) and serum creatinine. If the recheck is outside the limits of eligibility, the patient may not receive protocol therapy and will be considered off protocol therapy. See Section 7.1 for required studies to be obtained prior to starting protocol therapy.

INCLUSION CRITERIA

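### The primary analysis is labelled intention to treat but covers only eligible patients with IFI data, and no all-randomized analysis is planned

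*Combined protocol and SAP*

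**What the plan says.** Section 9.3.4 bases the primary analysis on the arm assigned at randomization, whatever the later compliance, and calls this intention to treat. The next sentence sets the population: "All eligible and randomized patients with available IFI data will be included in this analysis". Section 9.3.1 repeats the data condition for patients who stop prophylaxis early. Death, withdrawal of consent for data, and loss to follow-up before Day +42 are censored. The only other population named is an exploratory one limited to compliers, which is narrower still.

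Removal of ineligible patients is built into the sample size: "Considering up to 5% of the enrolled patients might be deemed ineligible, the maximum enrollment number is adjusted to 590". Section 9.2 gives the same target as 560 eligible patients within 590 enrolled.

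Randomization happens at entry on study (3.1.6), treatment is open label (9.1), and prophylaxis may be projected to start up to five days after enrollment (3.1.4). The blinding in Sections 9.3.2 and 10.2 covers classification of IFI. No section says who decides that an enrolled patient was ineligible, when, or whether the arm is hidden from them.

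Eligibility itself is described in two ways. Section 3.2.2 admits any allogeneic donor, matched related donors included. Section 9.1 describes eligible patients as those with an unrelated donor or a mismatched family member.

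**The concern.** Intention to treat protects the comparison because nothing that happens after assignment decides who is counted. Here a patient's status as eligible can be revised after the arm is known at the site. If revision is more likely in one arm and is related to IFI risk, the groups are no longer comparable, and the log-rank result would not show it. A reader who sees the label would assume this cannot happen.

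The donor conflict adds to the problem. On the Section 9.1 description, matched related recipients enrolled properly under Section 3.2.2 could be ruled out of the primary analysis. The documents do not give their number, so on that reading 30 need not be a ceiling.

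**Working it through.** **Inputs (all Section 9.3.3).** Day 0 to Day 42 incidence "is 7% in the control patients (with fluconazole or voriconazole) and that the incidence of IFI is 2% with caspofungin prophylaxis"; 280 per arm, "to achieve 80% power at 2-sided alpha level of 0.05". On the test: "The power consideration is based on a 2-sample log rank test", with exponential times. On loss: "A 5% exponential loss-to-follow-up during the at-risk period is also included in the power consideration".

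**1. The plan's own power.** Hazard ratio = ln(0.98)/ln(0.93) = 0.278. With event hazard λ and loss hazard μ over the 42 days, the expected event proportion is λ/(λ+μ) × [1 − exp(−(λ+μ))].
- Azole: λ = 0.0726, μ = 0.0513, giving 280 × 0.0683 = 19.1 events.
- Caspofungin: λ = 0.0202, giving 280 × 0.0195 = 5.5 events.
- Total 24.6 (25.2 without loss: 19.6 + 5.6).
- Freedman power: Φ(√24.57 × (1 − 0.278)/(1 + 0.278) − 1.96) = Φ(0.84) = 79.9%. The Lachin-Foulkes formula gives 80.1%. The stated 80% reproduces.

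**2. The excluded group.** 560/0.95 = 589.5, rounded up to 590; 590 − 560 = 30 patients. Assuming 15 per arm at the design rates, expected IFIs are 15 × 0.07 + 15 × 0.02 = 1.05 + 0.30 = 1.35. The chance of at least one is 1 − (0.93 × 0.98)^15 = 75%; of at least two, 39%.

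**3. How close to the line a result is likely to be.** Two-sample proportion test on Day 42 counts, 280 per arm, as a stand-in for the log-rank test:

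| Azole vs caspofungin events | p |
|---|---|
| 20 vs 6 (near the design expectation) | 0.005 |
| 20 vs 9 | 0.036 |
| 20 vs 10 | 0.061 |
| 16 vs 6 | 0.030 |
| 15 vs 6 | 0.045 |
| 14 vs 6 | 0.069 |

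From the expected result, significance at 0.05 is lost after 4 more caspofungin events or 6 fewer azole events. Section 9.3.5 plans two interim looks. Reading its spending function as α·t² (an assumption, since the printed symbol is incomplete), the final two-sided level is about 0.039, and 5 fewer azole events suffice. At the design rates, 13-14% of results lie within one event of the line and 26-28% within two, across the two thresholds.

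**4. Exclusion unrelated to arm and outcome.** In 400,000 simulated trials, 15 patients per arm were added back to 280, and the eligible-only and all-randomized conclusions were compared.

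| Assumed rates | Sets disagree at 0.05 | Sets disagree at 0.039 |
|---|---|---|
| 7% vs 2% (design) | 4.2% | 4.6% |
| 7% vs 3% | 7.0% | 7.0% |
| 5% vs 2% | 6.7% | 6.7% |

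With equal rates of 4.5% in both arms, the one-tail rejection rate at 0.05 is 2.4% eligible-only and 2.5% all-randomized, so neutral exclusion does not inflate it.

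**5. Power with everyone kept.** 24.57 × 295/280 = 25.9 events; Freedman power Φ(√25.89 × 0.5645 − 1.96) = Φ(0.91) = 81.9%, if excluded patients have the same rates and loss.

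**The case against.** The case for leaving the plan alone has four parts, and much of it stands.

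- Eligibility criteria mostly concern facts fixed before randomization. Section 3.2 says they are taken literally, cannot be waived and must be supported by source records. Removal on such facts, judged blind, would be close to neutral. This is right as far as it goes, but the plan does not say the judgement is blind.
- A reader might infer that a failed laboratory recheck between randomization and first dose removes a patient from the analysis. The documents do not support that. Section 3.2 says only that "the patient may not receive protocol therapy and will be considered off protocol therapy"; Section 8.1 lists this as a reason to leave therapy and requires continued follow-up with the IFI checklist; Section 7.1 keeps the study evaluations going; and Section 9.3.4 analyses patients regardless of compliance. The natural reading keeps them in, though the plan never says so outright.
- A reader might infer that patients with incomplete IFI follow-up are dropped. They are censored. Only those with no usable IFI data are left out, and censoring them at Day 0 would add nothing to the log-rank test.
- The 30 is an allowance of up to 5%, not a forecast.

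What remains is the group judged ineligible after assignment, for whom the label and the stated set do not agree.

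**Conclusion.** The point holds as a mismatch between label and analysis set, with a missing safeguard. Up to about 30 of 590 randomized patients, carrying about 1.35 of some 25 expected IFIs, may be excluded after open-label assignment, under a definition of eligible that conflicts between Sections 3.2.2 and 9.1.

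Two stronger readings are not supported. One is that one or two events generally decide this trial: at the expected result the margin is 4 to 6 events, and only about a quarter of results under the design rates fall within two events of the line. Even 15 vs 6 (p = 0.045) would miss a final level near 0.039. The other is that the exclusions inflate type I error: that would need exclusion related to arm and outcome, which the documents neither show nor guard against.

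The figures assume a 15/15 split of exclusions, the design rates unless stated otherwise, Day 42 proportions in place of the log-rank test, and the α·t² reading for the 0.039 level.

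**What to change.** - Define the primary set as all randomized patients analysed as assigned, keeping the existing censoring at the last IFI assessment.
- State that patients who fail a pre-dose laboratory recheck stay in the set.
- Run the eligible-only set as a sensitivity analysis, with eligibility judged blind to arm.
- Reconcile Section 3.2.2 with Section 9.1 so that eligible has one meaning.
- Tabulate by arm and reason all ineligible patients, patients not transplanted, and patients with no IFI data. The set should not be limited to patients who reach Day 0, because that too is a filter applied after randomization.
- If the eligible-only set stays primary, drop the unqualified intention-to-treat label and add the all-randomized analysis.

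The cost is SAP wording and one further analysis of patients already enrolled. The downside is that a few ineligible patients may slightly dilute the effect.
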